9.2. Setting

The study population includes adult patients aged 18 years or older diagnosed with non-small cell lung cancer who are carriers of the ALK gene rearrangement recruited in an 18-month estimated period from 20 high specialized hospitals at the country level who have started first-line therapy with lorlatinib according to label prescription, with treatment duration of at least 7 days and up to 28 days.

In Spain, molecular diagnosis of ALK rearrangement is routinely performed in patients with non-small cell lung cancer according to the diagnostic guidelines of the Spanish Society of Pathological Anatomy and the Spanish Society of Medical Oncology. Only patients with a confirmed and valid ALK testing will be included in our cohort. Among validated testing methods are the following: FISH fluorescence in situ hybridisation (FISH) Immnunohistochemistry using the D5F3 clon Roche VENTANA (IHC) mainly, PCR polymerase chain reaction (PCR) and the next generation sequencing (NGS)²³.

Given the estimated low incidence rate of 3.4% for this disease among the local population¹⁵, and the difficulty of performing molecular testing in some hospitals at the country level, the

Principal Investigators decided to involve centers specializing in the molecular diagnosis of ALK because otherwise, the lack of expertise in the molecular diagnostics would negatively impact the number of patients that can be enrolled in the study.

Based on data from the CROWN trial, where the incidence of CNS AEs was reported to be 42%, and assuming that the incidence could be higher in real clinical practice but potentially under-detected or recorded as grade 1 cases, they estimated that 116 patients treated with lorlatinib in first-line therapy for ALK+ non-small cell lung cancer are needed. This would provide 80% power to detect an incidence of 55% any grade CNS AEs using a 2-sided test.

Data collection Periods

Patient data will be collected in the following periods:

- **Pre-index period**: since diagnosis to start lorlatinib treatment.
- Index Date: date of start of lorlatinib.
- Post-index period: visits performed under clinical practice since index date and until
 end of study period

Patient data collection will cease at the end of study completion.

Study Visits

The study will be conducted in 5 visits, according to clinical practice:

- 1. **Baseline visit:** the day on which the patient fulfils the inclusion and exclusion criterion, including signature of the Informed Consent (i.e. the day on which the prospective observation starts) (within cycle 1 if lorlatinib)
- 2. Follow-up visit 1: will be scheduled at month 3 (third cycle of Iorlatinib)
- 3. Follow-up visit 2: will be scheduled at month 6 (sixth cycle of Iorlatinib)
- 4. Follow-up visit 3: Follow-up visit at month 12 (twelfth cycle of lorlatinib)
- 5. Final Visit: end of follow-up (end of data collection expected November 2027)

Data collection overview

Study Visits and Assessments	Baseline			FU3 C12D1	Final Visit
Informed consent	X				
SOCIO DEMOGRAPHIC DATA					
Medical history	X				
Physical examination including Height and weight	X	X	X	X	X

Study Visits and Assessments	Baseline	FU1	FU2	FU3	Final
		C3D1	C6D1	C12D1	Visit
Previous personal and family history of cancer	X				
CLINICAL DATA					
ECOG	X	X	X	X	X
Laboratory: Hematology and Blood chemistry (dyslipemia profile included). According to routine clinical practice	X	X	X	X	X
Comorbidities since Index Date: Charlson Index	X	X	X	X	X
Concomitant treatment(s) including previous history of Thromboembolic Disease	X	Х	X	X	X
Information of baseline tumor diagnosis: date, staging, (TNM),biopsy, PD-L1 expression, other mutations, etc	X				
Information regarding advanced disease: date, staging, metastatic location, CNS metastasis, previous systemic chemotherapy, radiotherapy, etc	X				
Previous systemic chemotherapy (Yes/No)	X				
Assessments CT scan	X				
Assessments brain MRI	X				
LORLATINIB TREATMENT					
Start, Stop and Discontinuation date	X	X	X	X	X
Dose by cycle	X	X	X	X	X
Reason for discontinuation or for dose reduction	X	X	X	X	X
Evaluation of Treatment Response: method (CT scan, MRI, others) and response	х	Х	X	X	X
AFTER LORLATINIB TREATMENT					

Study Visits and Assessments		FU1	FU2	FU3	Final
		C3D1	C6D1	C12D1	Visit
Post-progression treatment: type and palliative care					X
Date of death or last follow-up or last contact					X
QUALITY OF LIVE					
EORTC QLQ C30, LC13	X	X	X	X	X
SAFETY					
PRO-CTCAE	X	X	X	X	X
Adverse Events	X	X	X	X	X

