At a median of follow up of 60.2 months⁴ (95% CI, 57.4 to 61.6) in the lorlatinib group and 55.1 months (95% CI, 36.8 to 62.5) in the crizotinib group. The HR for PFS or death with lorlatinib versus crizotinib was 0.19 (95% CI, 0.13 to 0.27). Median PFS was NR (95% CI, 64.3 to NR) with lorlatinib and 9.1 months (95% CI, 7.4 to 10.9) with crizotinib. The 4- and 5-year PFS was 63% and 60% (95% CI, 51 to 68) with lorlatinib, respectively, and 10% and 8% (95% CI, 3 to 14) with crizotinib. Among patients with baseline brain metastases (measurable and/or non-measurable; n = 35 in the lorlatinib group and n = 38 in the crizotinib group), the HR for PFS or death with lorlatinib versus crizotinib was 0.08 (95% CI, 0.04 to 0.19); median PFS was NR (95% CI, 32.9 to NR) with lorlatinib and 6.0 months (95% CI, 3.7 to 7.6) with crizotinib. Five-year PFS was 53% (95% CI, 35 to 68) with lorlatinib and not evaluable with crizotinib as all patients had progression or death or were censored within 2 years. Among patients without baseline brain metastases, the HR for PFS or death with lorlatinib versus crizotinib was 0.24 (95% CI 0.16 to 0.36); median PFS was NR (95% CI, 64.3 to NR) with lorlatinib and 10.8 months (95% CI, 9.0 to 12.8) with crizotinib. Five-year PFS was 63% (95% CI, 52 to 71) with lorlatinib and 10% (95% CI, 5 to 18) with crizotinib.

Regarding the safety profile of the drug, the median treatment duration was 57.0 months (IQR, 13.9-63.3) with lorlatinib and 9.6 months (IQR, 4.7-17.1) with crizotinib. Overall, 49 of 149 patients (33%) treated with lorlatinib and 36 of 142 (25%) treated with crizotinib had at least one dose reduction. The median relative dose intensity was 99% (IQR, 80-100) with lorlatinib and 99% (IQR, 91-100) with crizotinib. All-causality any-grade AEs occurred in all patients in the lorlatinib group and in 140 of 142 patients (99%) in the crizotinib group; grade 3/4 AEs occurred in 77% and 57% of patients, respectively. A higher rate of grade 3/4 AEs from any cause in the lorlatinib group compared to the crizotinib group was mostly due to hypertriglyceridemia (25% v 0%), hypercholesterolemia (21% v 0%), weight gain (23% v 2%), and hypertension (12% v 1) with lorlatinib, 23% of patients had dose reduction, 62% had temporary treatment interruption, and 11% had permanent discontinuation because of AEs from any cause. Treatment-related AEs caused

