2. rwDuration of Response (DoR)	2. To determine real world duration of response (DOR), as the time from the first occurrence of a documented objective response to disease progression or death from any cause, whichever occurs first, as determined by the investigator according to RECIST v1.1. criteria (or Time from first documentation of CR or PR (whichever occurs first) after index until death or PD)			
3. rwDuration of Treatment (DoT)	3. To determine duration of treatment (DoT) as the time from lorlatinib's first dose to last dose for any cause. (Time to treatment discontinuation or Time from first dose to last dose of a treatment)			

4.	rwTime to next therapy/treatment (TTNT)	4.	To determine Time to next therapy/treatment (TTNT) as the Time from end of lorlatinib treatment to institution of next therapy	
5.	rwSystemic and intracranial Objective Response rate (ORR) using RECIST v1.1. criteria.	5.	To determine the systemic and real-world intracranial objective response rate (ORR) as determined by the investigator using RECIST v1.1. criteria	
6.	rwTime to intracranial progression rate at 12 and 18 months with and without brain metastasis at baseline	6.	Real world Time to intracranial progression rate at 12 and 18 months with and without brain metastasis at baseline	
7.	rwCumulative incidence of brain metastases (BM) in ITT population at 12 and 18 months (with and without baseline BM)	7.	Real world Cumulative incidence of brain metastases (BM) in ITT population at 12 and 18 months (with and without baseline BM)	
8.	rwOverall survival (OS) rate at 12 and 18m	8.	To determine the real-world overall survival (OS) rate at 12 and 18 months. OS is defined as the time from enrollment to death from any cause	
To evaluate the impact of lorlatinib on patients' quality of life.		of Pl Lo ar	hange from baseline in health-related quality f life (HRQoL), using the EORTC C30, RO_CTCAE (for CNS AEs) and submodules C13 at baseline, C1D15, C2D1, C3D1, C6D1 and every 3 months until the 1st year and then very 6 months	
To describe ALK testing methods used		Describe the different methods used to testing ALK mutations		
Exploratory Objectives (up to 30 patients)			Corresponding Endpoints	
To identify neuroimaging markers (MRI) that are predictive of the occurrence of CNS AEs		Fazekas scale, morphometric and radiomic analysis of baseline magnetic resonance images (MRIs) to identify imaging markers associated with the development of CNS AEs		

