9.3. Variables

Variable	Role	Data source(s)	Operational definition
Safety			
· //		Investigators Patient clinical record/Electronic Health record (EHR)	 Adverse Event: An AE is any untoward medical occurrence in a patient administered to a medicinal product. Serious Adverse Event: An SAE is any untoward medical occurrence in a patient administered a medicinal or nutritional product (including pediatric formulas) at any dose that: Results in death Is life-threatening Requires inpatient hospitalization or prolongation of hospitalization (see below for circumstances that do not constitute SAEs) Results in persistent or significant disability/incapacity (substantial disruption of the ability to conduct normal life functions) Results in congenital anomaly/birth defect

Variable	Role	Data source(s)	Operational definition
rwPFS rate at 12 and 18 months in the ITT population with and without brain metastasis at baseline.	Outcome measures	Investigators Patient clinical record/Electronic Health record (EHR)	To determine real-world progression-free survival (rwPFS) defined as the time from enrollment to the first occurrence of disease progression (intracranial or systemic) or death from any cause, whichever occurs first, as determined by the investigator using RECIST v1.1. criteria, at 12 and 18 months, in the ITT population with and without brain metastasis at baseline
rwDuration of Response (DoR)	Outcome measures	Investigators Patient clinical record/Electronic Health record (EHR)	To determine real world duration of response (DOR), as the time from the first occurrence of a documented objective response to disease progression or death from any cause, whichever occurs first, as determined by the investigator according to RECIST v1.1. criteria (or Time from first documentation of CR or PR (whichever occurs first) after index until death or PD)
rwDuration of Treatment (DoT)	Outcome measures	Investigators Patient clinical record/Electronic Health record (EHR)	To determine duration of treatment (DoT) as the time from lorlatinib's first dose to last dose for any cause. (Time to treatment discontinuation or Time

Variable	Role	Data source(s)	Operational definition
			from first dose to last dose of a treatment)
rwTime to next therapy/treatment (TTNT)	Outcome measures	Investigators Patient clinical record/Electronic Health record (EHR)	To determine Time to next therapy/treatment (TTNT) as the Time from end of lorlatinib treatment to institution of next therapy

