Imaging method for brain metastasis screening	patient's characteristics	Investigators Patient clinical record/Electronic Health record (EHR)	• (CT/MRI/None/Unknown)
Brain metastases present at time of lorlatinib initiation	patient's characteristics	Investigators Patient clinical record/Electronic Health record (EHR)	• Yes/No
Previous treatments for brain metastasis	patient's characteristics	Investigators Patient clinical record/Electronic Health record (EHR)	 Concomitant steroid treatment (Yes/No) Symptomatic (Yes/No) List

Variable	Role	Data source(s)	Operational definition
Surgery	Baseline patient's characteristics	Investigators Patient clinical record/Electronic Health record (EHR)	Yes/No. Date
Whole brain radiation Yes/No (Date of last dose)	Baseline patient's characteristics	Investigators Patient clinical record/Electronic Health record (EHR)	• (Date of last dose)
SRS/radiosurgery	Baseline patient's characteristics	Investigators Patient clinical record/Electronic Health record (EHR)	Yes/No (Date of last dose
Has the patient participated in a clinical trial previously?	Baseline patient's characteristics	Investigators Patient clinical record/Electronic Health record (EHR)	• (Yes/No/Unknown)
Previous radiotherapy	Baseline patient's characteristics	Investigators Patient clinical record/Electronic Health record (EHR)	• (Yes/No)
Intention of previous radiotherapy	Baseline patient's characteristics	Investigators Patient clinical record/Electronic Health record (EHR)	Curative, palliative

Variable	Role	Data source(s)	C	perational definition
Location of previous curative radiotherapy	Baseline patient's characteristics	Investigators Patient clinical record/Electronic Health record (EHR)	•	Chest, bone, brain, others (specify
Previous systemic chemotherapy	Baseline patient's characteristics	Investigators Patient clinical record/Electronic Health record (EHR)	•	Yes/No
Previous systemic chemotherapy Intention	Baseline patient's characteristics	Investigators Patient clinical record/Electronic Health record (EHR)	•	Curative (adjuvant or neoadjuvant)
Previous systemic chemotherapy Regimen used	Baseline patient's characteristics	Investigators Patient clinical record/Electronic Health record (EHR)	•	List
Clinical data during t	reatment with le	orlatinib		
Start and end of treatment	notiont's	Investigators Patient clinical record/Electronic Health record (EHR)	•	Date from the first lorlatinib treatment taken and last

Variable	Role	Data source(s)	Operational definition

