Height at tumor progression	patient's characteristics	Investigators Patient clinical record/Electronic Health record (EHR)	• Meters
Weight at tumor progression	patient's	Investigators Patient clinical record/Electronic Health record (EHR)	• kg
Post-progression treatment	patient s	Investigators Patient clinical record/Electronic Health record (EHR)	• Yes/No
Post progression treatment Type	patient's characteristics	Investigators Patient clinical record/Electronic	Chemotherapy, TKI (specify type), Immunotherapy,

Variable	Role	Data source(s)	Operational definition
		Health record (EHR)	Radiotherapy, Palliative Care.
Post progression treatments	On-treatment patient's characteristics		Describe subsequent treatment
Clinical data after lorlatinib completion			
Alive: Yes/No	After- treatment data	Investigators Patient clinical record/Electronic Health record (EHR)	• Yes/No
Date of death or last follow-up	After- treatment data	Investigators Patient clinical record/Electronic Health record (EHR)	Date format

Variable	Role	Data source(s)	Operational definition
Participant's perspective			
EORTC QLQ-C30	Outcome measure	Baseline, C3D1, C6D1, C12D1, Final visit	ePRO (through mobile device) questionnaire containing 30 questions and assesses the quality of life of oncological participants multidimensionally over 10 subscales.
EORTC QLQ-LC13	Outcome measure	Baseline, C3D1, C6D1, C12D1, Final visit	ePRO (through mobile device) questionnaire for lung participants. The QLQ-LC13 incorporates one multi-item scale to assess lung cancerassociated symptoms (i.e.coughing, haemoptysis, dyspnoea and pain) and side- effects from conventional chemo- and radiotherapy.
PRO-CTCAE (only for CNS AEs)	Outcome measure	Baseline, C3D1, C6D1, C12D1, Final visit	ePRO (through mobile device) questionnaire. When referring to CNS (Central Nervous System) adverse events, the PRO-CTCAE helps in assessing symptoms such as headaches, dizziness, and cognitive changes, which are crucial for understanding the impact of cancer treatments on the nervous system.

Variable	Role	Data source(s)	Operational definition
Exploratory variables (30 patients expected)			
To identify neuroimaging markers (MRI) that are predictive of the occurrence of CNS AEs	Exploratory analysis	MRI	Fazekas scale, morphometric and radiomic analysis of baseline magnetic resonance images (MRIs) to identify imaging markers associated with the development of CNS AEs.

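### Time to next therapy has no specified end date, and its source fields are labelled for use only after progression

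*Protocol*

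**What the plan says.** The endpoint table in Protocol section 9.1 defines TTNT as "Time from end of lorlatinib treatment to institution of next therapy". The variables table in section 9.3 lists TTNT as an outcome measure taken from investigators and the health record, with the same definition: "as the Time from end of lorlatinib treatment to institution of next therapy". Neither place limits it to patients who progressed.

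The items that would feed it are these:

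- **Section 9.2, data collection overview, block after lorlatinib:** "Post-progression treatment: type and palliative care", ticked at the Final Visit only. The only dates in that block are those of death, last follow-up or last contact.
- **Section 9.3:** a post-progression treatment item (Yes/No), a type item beginning "Chemotherapy, TKI (specify type), Immunotherapy", and a further post-progression row reading "Describe subsequent treatment". All three stand under clinical data during lorlatinib treatment. The block for data after lorlatinib holds only vital status and the date of death or last follow-up.

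The starting point of TTNT is covered: section 9.3 asks for "Date from the first lorlatinib treatment taken and last", and section 9.2 has stop and discontinuation dates at every visit.

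**The concern.** TTNT needs two dates, and the protocol specifies only the first. The fields nearest the second are also conditional, by their label, on progression, while the endpoint is not.

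Section 9.3 offers toxicity and other causes, beside progression, as reasons for stopping. Section 10.3 names unacceptable toxicity, intercurrent illness and refusal among the grounds. A patient who stops for one of these and moves to another drug without progressing has a TTNT event by definition but no field for it. Three things could then happen:

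- The patient is left out of TTNT.
- The patient is entered as having had no post-progression treatment and is censored although the event occurred, which lengthens the estimated TTNT.
- The patient progresses later, and the field records the treatment given then, which need not be the first therapy after lorlatinib.

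In each case TTNT would describe mainly progressors. In a study whose main interest is tolerability, patients who switch because of toxicity are a group the endpoint should keep. An SAP cannot supply a date that was never collected.

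**Working it through.** The protocol states no figure for this point, so the main check sets what TTNT needs against what is listed.

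| Needed for TTNT | Listed in 9.2 or 9.3? |
|---|---|
| End of lorlatinib | Yes: stop and discontinuation dates at each visit (9.2); first and last treatment dates (9.3) |
| Start of next therapy | No item in either table |
| Next therapy after a stop for any reason | No: every next-therapy item is labelled post-progression |

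Two other listed dates cannot stand in for the missing one. The row on treatment after progression carries a date of definitive discontinuation, which is a stop date. The progression date does not serve either, because section 10.3 allows treatment to continue beyond radiological progression.

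**Scale of the progression-only label (illustration).**

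Inputs:
- 116 patients (section 9.5).
- Recruitment June 2025 to November 2026 and data close in November 2027 (section 6), so follow-up runs from 12 to 30 months.
- CROWN lorlatinib treatment duration: median 57.0 months, lower quartile 13.9 months (section 7).
- CROWN permanent stops for treatment-related adverse events: eight patients, 5%, all in the first 26 months (section 7).

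Assumptions: even accrual and exponential stopping at rate λ. The expected proportion stopped by data close is

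1 − [exp(−12λ) − exp(−30λ)] / (18λ).

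- From the median: λ = ln 2 / 57.0 = 0.01216 per month. Proportion = 1 − (0.8642 − 0.6943)/0.2189 = 0.224, and 116 × 0.224 ≈ 26 patients.
- From the lower quartile: λ = −ln 0.75 / 13.9 = 0.02070 per month. Proportion = 1 − (0.7801 − 0.5375)/0.3725 = 0.349, and 116 × 0.349 ≈ 40 patients.

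Stops for treatment-related adverse events: 116 × 0.05 = 5.8, about 6 patients.

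Share of all stoppers: 5.8/40 = 14.5% to 5.8/26 = 22.3%, or roughly 15–22%.

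**Cross-check on the longer horizon.** Section 7 also reports for lorlatinib that "11% had permanent discontinuation because of AEs from any cause", a figure from about five years of follow-up: 116 × 0.11 = 12.8. The matching denominator is the number stopped by 60 months, 116 × (1 − exp(−60λ)), which is about 60 (median rate) to 82 (quartile rate). The share is 12.8/82 = 16% to 12.8/60 = 21%, close to the range above.

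**The case against.** The strongest reply is that TTNT is itself a row in section 9.3, sourced from the investigator and the health record, with an operational definition that contains the start of the next therapy. A site or eCRF designer could read that row as an obligation to obtain the date. The table is also not a field-level specification: it gives best response without the date of first response, which duration of response needs, and brain progression as Yes/No without a date, which time to intracranial progression needs. The eCRF and the Data Management Plan are still to be built, and a site could write a date in the description item.

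Much of this stands. A reader might infer that TTNT cannot be calculated at all, or that the end date will be missing for every event. The documents do not support that; they show only that no listed item requires the date. Nor does the definition exclude patients who switch for toxicity. Any loss would come through the field labels.

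Three other inferences also go too far:

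- Setting 12.8 against 26 gives 49%, as if half of all stoppers were affected. That divides a five-year count by stoppers over 12 to 30 months.
- The primary endpoint in section 9.1 covers adverse events, dose reductions and concurrent medication used to control them. The next anticancer drug is not part of it, so the primary objective is not compromised.
- Recording only at the Final Visit is no defect here, because a start date can be read from the medical record then.

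What the reply does not remove is the mismatch. The definition applies after any stop, every next-therapy item says post-progression, and none names a start date. Section 9.7 aims to keep collection to critical data elements, so an unlisted field could easily be left out of the eCRF.

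**Conclusion.** The point holds as a gap between an endpoint and the data listed to support it. The end date of TTNT is not among the specified items, and the next-therapy items are labelled for progressors only. Followed as written, TTNT would rest mainly on patients who progressed. This conclusion comes from comparing sections 9.1, 9.2, 9.3 and 10.3 and needs no numerical assumption.

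The size of about 6 patients, or roughly 15–22% of 26–40 stoppers, is for scale only. It assumes that CROWN stopping rates carry over to this population, that accrual is even and stopping exponential, and that each patient who stops for a treatment-related adverse event starts another therapy before progression. The documents give no figure for that last step, so the true number could be lower. The 26-month window is also longer than the 21-month average follow-up, (12 + 30)/2, which again points to a somewhat lower count.

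One secondary effectiveness endpoint is affected. The change should be made before the eCRF is fixed, but the primary safety description does not depend on it.

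**What to change.** In the section 9.2 data collection overview and in section 9.3, replace the post-progression treatment items with one item, first subsequent anticancer therapy after lorlatinib. Record Yes/No, start date, type, and reason for the switch (progression, adverse event, other). Complete it for every patient who permanently stops lorlatinib, whatever the reason, and place it in the section 9.3 block for data after lorlatinib. It can stay at the Final Visit and be read from the record.

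The cost is a few eCRF fields in a block that sites already complete. No procedure or visit is added.
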